Date: April 9, 2019

Title: Importance of Sock Type in the Development of Foot Lesions on Low-difficulty, Short Hikes.

Description of document: Materials and Methods (Study Protocol: description of the clinical study, including objective and design. Statistical Analysis Plan (description of the statistical considerations for analyzing the data collected in the study.) results of the study (Results obtained in the study) and Supplementary data (protocol of measures and other tables).

Materials and Methods

1. Permission and participants

All participants signed an informed consent form, and permission for the study was obtained from the Bioethics Committee (reference 126/2016). The admission criteria were: be of legal age, have no current health problems that would hinder or prevent participation in the hike, and carry a backpack weighing less than 3 kg. Participants were asked to use specific hiking footwear (light, flexible, soft-soled, with good grip and breathable material) (low top hiking shoes), based on earlier studies [38-40]. They were also asked to do the entire hike following the instructions of an experienced guide and to not remove their footwear or socks before examination by a podiatrist.

2. Sock type and interventions performed

Socks were of two types: technical socks, designed for high performance sports use (Lurbel brand, models Tierra and Set), and non-technical socks for everyday use. The socks had different composition: Tierra (50% regeneractiv, 25% cool-teak, 17% polyamide ions, 8% lycra); Set (75% cotton, 17% polyamide, 8% lycra) and cotton (98% cotton, 2% elastane). The technical socks had reinforced weave in the toe, metatarsal and heel areas.

Participants were examined by trained podiatrists on three occasions to measure the study variables: at the start of the walk (km 0), at the end of the asphalt section (half way; km 14.5) and at the end (km 29.6). The protocol of measures was followed (supplementary data).

3. Study design, route description and participants

Weight (kg)

A clinical trial randomized, double blinded was designed to analyze the influence of different types of socks (technical and non-technical) on the appearance of foot injuries after a low-difficulty, short-term sport activity. The study follow the CONSORT criteria.

To carry out the study, the hiker was previously registered. The researchers contacted the participants to explain the study. In addition, data on age, sex, foot number and associated diseases that prevented the completion of the route were obtained. One hour before starting the route, researchers who did not intervene in the exploration process, made registration and delivery to each hiker of two technical socks (1 Set and 1 Tierra) appropriate to the size of the foot and randomly for the right foot (RF) and left foot (LF). Likewise, it proceeded for non-technical socks (cotton), but in this case both feet wore the same type of sock. All the participants before the initial exploration had their socks put on for half an hour. The hike was low-difficulty, over a short distance [37]. The first 14.5 km were on asphalt and the last 15.1 km on dirt. The height range was 189 m and the pace was moderate, at 5 km/hour. The sample comprised 109 participants (53 men and 56 women). Two women had to give up the hike for personal reasons. Both wore technical socks.

The Table 1 explain the anthropometric characteristics of the participants and the distribution of the socks, differentiating by sex and feet.

Anthropometric variable	Total	Male	Female	
Gender		48.6%	51.4%	
Age (years)	44± 25	49± 21	36 ± 24	
Height (meters)	1.7± 0.1	1.7± 0.1	1.6± 0.1	

81.0±13.5

61.4±7.8

68.8±19.4

Table 1. Anthropometric variables, total sock distribution and sock distribution by gender.

BM	II	24.9± 3.6	26.6± 3.7	23.5± 9.1
Sock type di	istribution	Total %	Male %	Female %
LF sock	Tierra	40.4 (n=44)	35.8 (n=19)	44.6 (n=25)
	Set	29.4 (n=32)	35.8 (n=19)	23.3 (n=13)
	Cotton	30.2 (n=33)	28.4 (n=15)	32.1 (n=18)
RF sock	Tierra	29.4 (n=32)	35.8 (n=19)	23.3 (n=13)
	Set	40.4 (n=44)	35.8 (n=19)	44.6 (n=25)
	Cotton	30.2 (n=33)	28.4 (n=15)	32.1 (n=18)

Km=Kilometres, n=sample size, %=Percentage, ±=Standard deviation, kg=Kilogrammes, BMI=Body mass index, LF=Left foot, RF=Right foot.

4. Study variables

The qualitative variables analysed were: gender, body mass index (BMI) by rank, sock type, dermal lesions (all lesions developed during the hike, both keratopathies with keratinisation disorder and dermatopathies without keratinisation disorder), muscle lesions (all lesions developed during the hike) and nail lesions (all nail lesions developed during the hike, both traumatic and non-traumatic onychopathies). The height and weight data obtained were used to calculate BMI by rank, interpreted according to the World Health Organization classification [41] (Table 2).

Table 2. Qualitative variables and categories. BMI= Body mass index.

Qualitative variable	Category	
Gender	Male Female	
BMI	Underweight (<18.5) Normal weight (18.5-24.99) Overweight (25.0-29.9) Obese ((>30)
Sock type	Technical (Tierra) Technical (Set) Non-technical (Cotton)	
Skin lesion	Blister Injury (Erosion & chafing) Reddened skin Urticaria Crevice H	Ieloma
Muscle lesion	Pain due inadequate warm Inflammation Muscle discomfort Sprain	
Nail lesion	Onychocryptosis Subungueal hematoma	

The quantitative variables analysed were: age, body mass index (BMI), temperature of each foot measured in two aspects (plantar and dorsal), and perimeter of each foot, measured in four areas (dorsal aspect of toes, instep, heel, tibia).

5. Measuring instruments

The height range and the pace hikers was controlled with a Garmin ETREX 20X GPS (Global Positioning System). Perimeter was measured with a flexible, non-elastic tape measure (Lawton 18-0160, precision 1 mm). Weight was measured using scales (Tanita UM-076, precision 0.1kg) and height was measured using the weight rod of different scales (SECA 704, precision 1 mm).

Temperatures were taken with an infrared thermometer (FTN Medisana, precision 0.18° C), calculating the mean of the three measurements. An intra rate of the measure was done to detect the error of the measure of the temperature, obtaining an error of 0.1452.

6. Statistical tests

The data were analysed using IBM SPSS Statistics for Windows, Version 22.0 (IBM, Armonk, New York). The statistical treatment consisted of data study and cleansing, descriptive variable analysis, normality test (Shapiro-Wilks test). The studies of normality were no significant (p-values between 0.000 y 0.044).

Quantitative variables depending on whether the samples were paired or independent, Friedman's test for related samples and Kruskal-Wallis was performed for independent samples, both with Bonferroni correction for multiple testing was applied. For the qualitative variables the

chi-square or Fisher's exact test with a significance level of α = 0.05 was carried out. The variables analysed by logistic regression were quantified using the ODDS Ratio (OR). The effect size for the different variables was also calculated. First, for Kruskall-Wallis tests, the variation was between 0.443 y 0.888, and for Friedman tests, the variation was between 0.336 y 0.623. Therefore, in both cases the effect size could be considered median and high.

All p-values = 0.000 are less than 1 per 1000.

Results

After completing the first part of the hike, the most frequent dermal lesions among participants were blisters and erosions.

Table 3. Prevalence of skin, muscle and nail lesions during the 0-14.5 km of the hike by sex.

(0.14 = 1)				Fen	nale					Ma	ıle		
(0-14.5 km)		Tier	ra %	Se	et %	Cott	on %	Tier	ra %	Set	%	Cott	on %
Skin lesion	%Tt.	RF	LF	RF	LF	RF	LF	RF	LF	RF	LF	RF	LF
Blister	12.8	0.0	4.0	8.0	7.7	22.2	27.8	0.0	5.3	5.3	0.0	6.7	13.3
Erosion	2.8	0.0	0.0	0.0	0.0	11.1	5.6	0.0	0.0	0.0	0.0	6.7	0.0
(0.44.5.1)				Fer	male					Ma	ıle		
(0-14.5 km)		Tier	ra %	Se	et %	Cott	on %	Tier	ra %	Set	%	Cott	on %
Muscle lesion	%Tt.	RF	LF	RF	LF	RF	LF	RF	LF	RF	LF	RF	LF
Pain due inadequate warm	21.1	23.1	27.8	8.0	7.7	27.8	27.8	10.5	15.8	10.5	0.0	13.3	13.3
Inflammation	2.8	0.0	4.2	4.0	0.0	0.0	0.0	0.0	10.5	10.5	0.0	0.0	0.0
Muscle discomfort	1.8	0.0	0.0	0.0	0.00	0.0	0.0	5.3	5.3	0.0	0.0	0.0	0.0

Km=Kilometres, %=Percentage, Tt=Total, RF=Right foot, LF=Left foot.

None of the other dermal lesions included in the evaluation (reddened skin, urticaria, crevice and heloma) were detected. Significant differences were found between the percentage of dermal lesions in hikers wearing technical socks (6.6%) and non-technical socks (36.4%) (p-value=0.000). The women had a higher percentage of dermal lesions (23.2%) than the men (7.5%) (p-value=0.034), regardless of sock type. Moreover, the percentage of women with dermal lesions was significantly higher among wearers of non-technical socks (50%) than in wearers of technical socks (10.5% had lesion) (p-value=0.002). Particularly the women presented more blisters in both RF and LF when they wore cotton sock compared to the Tierra and Set socks (RF p-value = 0.050, LF p-value = 0.042). In the case of men, there was no difference in any of the skin lesions at 14.5 km on any foot compared to the sock used (Table 3). The most frequent muscle lesions at the end of the first part of the hike were pain due inadequate warm (21.1%), inflammation (2.8%) and muscle discomfort (1.8%). No sprains or nail disorders were detected at the end of the first part of the hike. No difference between any of muscle lesions analyzed and technical and non-technical socks were found. By sex, no differences were found regarding technical and non-technical socks or concerning the model used sock on each foot (Table 3).

Table 4. Prevalence of skin, muscle and nail lesions during the 14.5-29.6 km of the hike by sex.

(14.5-29.6 km)				Fema	ale					N	I ale		
(14.5-29.6 KM)		Tie	rra %	Set	%	Cott	on %	Tier	ra %	Se	et %	Cott	on %
Skin lesion	%Tt.	RF	LF	RF	LF	RF	LF	RF	LF	RF	LF	RF	LF
Blister	19.6	7.7	12.0	20.0	7.7	25.0	12.5	5.3	0.0	5.3	21.1	6.7	0.0
Erosion	7.5	0.0	4.0	8.0	0.0	12.5	18.8	0.0	0.0	0.0	0.0	20.0	13.3
Reddened skin	3.7	0.0	0.0	0.0	0.0	18.8	18.8	0.0	0.0	0.0	0.0	6.7	6.7
Urticaria	0.9	0.0	0.0	0.0	0.0	6.3	6.3	0.0	0.0	0.0	0.0	0.0	0.0
Crevice	0.9	0.0	0.0	0.0	0.0	0.0	0.0	0.0	0.0	0.0	0.0	6.7	0.0
Heloma	0.9	0.0	0.0	0.0	0.0	0.0	0.0	0.0	0.0	0.0	0.0	6.7	6.7
(14.5-29.6 km)			Female			Male							

		Tier	ra %	Set	t %	Cott	on %	Tier	a %	Se	et %	Cott	on %
Muscle lesion	%Tt.	RF	LF	RF	LF	RF	LF	RF	LF	RF	LF	RF	LF
Pain due inadequate warm	11.2	15.4	4.0	4.0	7.7	0.0	12.5	10.5	0.0	5.3	10.5	0.0	0.0
Inflammation	0.9	0.0	4.0	4.0	0.0	0.0	0.0	0.0	0.0	0.0	0.0	0.0	0.0
Muscle discomfort	0.9	0.0	0.0	0.0	0.0	0.0	0.0	0.0	0.0	5.3	0.0	0.0	0.0
Sprain	0.9	0.0	0.0	4.0	0.0	0.0	0.0	0.0	0.0	0.0	0.0	0.0	0.0
(14.5-29.6 km)				Fem	ale					N	Iale		
(14.5-29.0 KIII)		Tier	ra %	Set	t %	Cott	on %	Tierr	a %	Se	et %	Cott	on %
Nail lesion	%Tt.	RF	LF	RF	LF	RF	LF	RF	LF	RF	LF	RF	LF
Onychocryptosis	0.9	7.7	0.0	0.0	0.0	0.0	0.0	0.0	0.0	0.0	0.0	0.0	0.0
Subungual hematoma	1.9	0.0	0.0	0.0	0.0	6.3	6.3	0.0	0.0	0.0	0.0	6.7	6.7

Km=Kilometres, %=Percentage, Tt=Total, RF=Right foot, LF=Left foot.

In the second part of the hike, a greater variety of dermal lesions was detected. The most prevalent were blisters, erosions and reddened skin. Again, no urticaria, reddened skin, crevices, or helomas were detected with either technical sock. Differences were found between the percentage of dermal lesions among hikers wearing technical socks (21.1%) or non-technical socks (54.8%) (p-value=0.001). By gender, the percentage of women and men with dermal lesions was higher among wears of non-technical socks (women 68.8% and men 40%) than among wearers of technical socks (women 26.3% and men 15.8%) but the differences only were significant in women (p-value=0.006). Considering the sock used in each foot, in the case of women, presented more reddened skin in both RF and LF if they used cotton sock compared to the Tierra and Set (RF and LF p-values=0.023). In the case of men, they presented more blisters in the LF if they used Set sock than cotton or Tierra (p-value=0.021) and more erosion in the RF if they used cotton sock in comparison with the Tierra or Set (p-value=0.018) (Table 4). A greater variety of total muscle lesions was also detected in the second part of the hike: pain due to inadequate warm, inflammation, muscle discomfort and sprain. No differences were found between any of the muscular injuries analysed and the technical and non-technical socks neither by sex (Table 4).

Nail lesions like onychocryptosis (0.9%) and subungual hematomas (1.9%) were infrequently and developed only in the second part of the hike. No difference between any of the nail lesions analyzed and technical and non-technical socks were found. By sex, no differences were found (Table 4).

The temperature comparisons between technical and non-technical socks, regardless of distance, foot, measurement area and sex, showed significant differences. The Friedman test was performed (p value <0.005) for the comparisons between paired samples and the Kruskal-Wallis test was performed (p value <0.009) for independent samples. (Supplementary data, tables A, B).

The differences in temperature are greater at the beginning of the hike than at the end. An increase in temperature from 0 km to 14.5 km was observed, and temperature stabilization of 14.5 km to 29.6 km in all types of socks. However, the increase in temperature, from the beginning to the end of the hike, varies between the types of socks in all the areas measured at the foot of the walkers; being superior when using non-technical socks (about 8.5°C) than in the case of using technical socks (about 1.2°C) (Supplementary data, tables A, B).

Table 5. Women's foot temperature by sock type.

					FEMAL	E			
Distance	Sock P-value sock			P-	value distanc	e			
(km)	Т	S	С	T-S	T-C	S-C	T	S	С
				Dor	sal temp (°C) RF			
0	34.7	35.0	19.9	1.000	0.000*	0.000*	(1)=0.002*	(1)=0.000*	(1)=0.001*
14.5	36.2	36.3	31.8	1.000	0.013*	0.000*	(2)=0.000*	(2)=0.000*	(2)=0.000*
29.6	36.3	36.3	30.6	1.000	0.000*	0.000*	(3)=1.000	(3)=1.000	(3)=0.867
				Dor	sal temp (°C) LF			
0	35.0	35.0	19.9	1.000	0.000*	0.000*	(1)=0.000*	(1)=0.005*	(1)=0.003*

14.5	36.4	36.2	32.2	0.931	0.002*	0.036*	(2)=0.000*	(2)=0.001*	(2)=0.000*
29.6	36.3	36.3	30.8	1.000	0.000*	0.000*	(3)=1.000	(3)=1.000	(3)=0.472
				Plan	tar temp ((ºC) RF			
0	34.8	34.8	20.5	1.000	0.000*	0.000*	(1)=0.007*	(1)=0.000*	(1)=0.000*
14.5	36.0	36.2	29.7	1.000	0.000*	0.000*	(2)=0.001*	(2)=0.000*	(2)=0.000*
29.6	36.2	36.2	30.6	1.000	0.000*	0.000*	(3)=1.000	(3)=1.000	(3)=1.000
				Plan	tar temp	(ºC) LF			
0	34.8	34.9	21.0	1.000	0.000*	0.000*	(1)=0.002*	(1)=0.009*	(1)=0.000*
14.5	36.2	36.0	30.2	0.287	0.000*	0.000*	(2)=0.000*	(2)=0.000*	(2)=0.000*
29.6	36.1	36.0	30.2	1.000	0.000*	0.000*	(3)=0.420	(3)=0.785	(3)=1.000

Km=Kilometres, T=Tierra, S=Set, C=Cotton, Temp=Temperature, (°C)=Degrees centigrade, RF=Right foot, LF=Left foot, (*)=Significant difference, (1)= Distance between 0-14.5 Km, (2)= Distance between 0-29.6 Km, (3)= Distance between 14.5-29.6 Km.

By gender, no significant differences were detected between technical socks models nor in women (p-values> 0.287) nor in men (p-values> 0.249). However, significant differences were detected between each model of technical socks and the non-technical sock for all distances and areas of the feet measured (Tierra-Cotton p-values<0.013 in women and p-value<0.036 in men) and (Set-Cotton p-values<0.036 in women and p-value<0.014 in men). Regarding the distance in both men and women, differences were observed from the beginning to the end and from the beginning to the middle route with all the models. In addition, in the case of men the tendency is observed in the plant of both feet to increase the temperature from the middle to the end of the hike (LF p-value=0.056, RF p-value=0.091) although it cannot be considered statistical significance (tables 5 and 6).

Table 6. Men's foot temperature by sock type.

					MAL	.E			
Distanc		Sock		P	-value sock]	P-value dista	nce
e (km)	T	S	С	T-S	T-C	S-C	Т	S	С
]	Dorsal temp	(°C) RF			
0	34.	35.1	22.0	1.000	0.000*	0.000*	(1)=0.005	(1)=0.017	(1)=0.003*
	9						*	*	
14.5	35.	36.1	32.9	1.000	0.030*	0.014*	(2)=0.000	(2)=0.000	(2)=0.000*
	9						*	*	
29.6	36.	36.4	30.0	1.000	0.000*	0.000*	(3)=0.470	(3)=0.223	(3)=0.896
	3								
]	Dorsal tem	p (ºC) LF			
0	35.	35.3	21.4	1.000	0.000*	0.000*	(1)=0.008	(1)=0.240	(1)=0.003*
	2						*		
14.5	36.	36.0	32.5	0.931	0.036*	0.002*	(2)=0.000	(2)=0.003	(2)=0.000*
	3						*	*	
29.6	36.	36.4	30.8	1.000	0.000*	0.000*	(3)=0.128	(3)=0.401	(3)=0.558
	5								
				I	Plantar tem	p (ºC) RF			
0	34.	35.1	22.0	1.000	0.000*	0.000*	(1)=0.011	(1)=0.017	(1)=0.004*
	9						*	*	
14.5	35.	36.4	30.3	0.249	0.007*	0.000*	(2)=0.000	(2)=0.000	(2)=0.001*
	8						*	*	
29.6	36.	36.4	29.0	1.000	0.000*	0.000*	(3)=0.091	(3)=0.223	(3)=1.000
	2								
				I	Plantar tem	p (ºC) LF			
0	35.	34.9	21.8	1.000	0.000*	0.000*	(1)=0.006	(1)=0.001	(1)=0.042*
	0						*	*	

14.5	36. 1	35.7	31.2	0.287	0.000*	0.000*	(2)=0.000	(2)=0.000	(2)=0.000*
29.6	36.	36.2	29.3	1.000	0.000*	0.000*	(3)=0.056	(3)=0.401	(3)=0.558

Km=Kilometres, T=Tierra, S=Set, C=Cotton, Dif.=Difference Temp=Temperature, (${}^{\circ}$ C)=Degrees centigrade, RF=Right foot, LF=Left foot, (*)=Significant difference, (1)= Distance between 0-14.5 Km, (2)= Distance between 0-29.6 Km, (3)= Distance between 14.5-29.6 Km.

The study of the perimeter of hikers' feet analysed in total and by gender, in relation to distance and sock type, did not reveal significant results (data not shown).

Table 7. Probability of suffering skin and muscle lesions in relation to anthropometric variables and sock type throughout the hike.

1	PROBABILITY SKI	N LESIONS	PROBABILITY M	USCLE LESIONS		
Dist	ance:	Distance: 14.5-29.6 Km	Distance: 0-14.5 Km			
96% If	female	90% If male	100% I	f male		
100% If non-	technical sock	100% If non-technical sock	67% If non-te	chnical sock		
Direct relation	Inverse relation	Inverse relation	Direct relation	Inverse relation		
BMI	Age	Age	BMI	Age		

km=Kilometre, %= Percentages, BMI=Body mass index.

It was possible to study the relation between variables and predict the probability of lesions developing during the hike using logistic regression analysis (Table 7). Women have a higher probability than men of suffering skin lesions in hikes of up to 14.5 km. However, men have a higher probability than women of suffering skin lesions on hikes of 14.5 to 29.6 km and muscle lesions on hikes of up to 14.5 km.

The non-technical socks showed the highest probability of wearers suffering dermal and muscle lesions, both from 0-14.5 km and from 14.5 km to the end of the hike. The probability of dermal and muscle lesions developing in relation to the quantitative variables showed direct and inverse relations. From 0-14.5 km, the BMI and age of hikers are directly and inversely related, respectively, both in dermal and in muscle lesions. In the second part of the hike, age continued to show an inverse relation with skin lesions, but no relation with BMI was identified (Table 7).

Supplementary data

Protocol of Measures. Top shows the protocol of measure at the starting point (0 km). Middle part includes the protocol of the first part of the hike (0-14.5 km) and lower part of the table reflex the measurement protocol of the second part of the hike (14.5-29.6 km)

PPOTOCOI	OF MEASURES
STARTING POINT (0 Km)	OF MEASURES
Dorsal Number: Gender: Gender:	Foot size Weight Size
Body mass index (BMI):	The state of the s
	Previous Alterations on skin, muscles or
nails	
	rature LF
Plantar Plantar	
Dorsal Dorsal	
Perimeters RF: (Three different measures)	Perimeters LF: (Three different measures)
tibia	tibia
hell	hell
toes instep	toes instep
FIRST PART OF THE HIKE (0-14.5 Km)	Perimeters RF: (Three different measures)
	tibia
Temperature RF: (Three different measures)	
Plantar	
Dorsal	hell
Temperature LF: (Three different measures)	
Plantar	
Dorsal	
	toes instep Perimeters LF: (Three different measures)
LESIONS (0-14.5KM)	27.0 1 1 1 1
SKIN LESIONS (SPECIFY RF AND LF)	tibia
Hyperkeratosis Heloma	
BlisterErosion Reeddned skin	hell
UrticariaGrevice Others	
MUSCLE LESIONS (SPECIFY RF AND LF)	
Pain due inadequate warmInflamation	
Muscle discomfortSprain Others	toes instep
NATI LECIONIC (CDECIEV DE ANID LE)	toes
NAIL LESIONS (SPECIFY RF AND LF)	
Onichocryptosissubungual hematoma Others	
Others	
EVED A DETAIL C	
EXTRA DETAILS	

SECOND PART OF THE HIKE (14.5-29.6 Km)	
Temperature RF: (Three different measures)	Perimeters RF: (Three different measures)
Plantar Dorsal	tibia
Temperature LF: (Three different measures)	hell
Plantar	
Dorsal	
LESIONS (14.5-29.6 Km) SKIN LESIONS (SPECIFY RF AND LF)	toes instep
HyperkeratosisBlisterErosionReeddned skin	
Urticaria	
GreviceOthers	
	Perimeters LF: (Three different measures)
MUSCLE LESIONS (SPECIFY RF AND LF) Pain due inadequate warm	tibia
Muscle discomfort Sprain Others NAIL LESIONS (SPECIFY RF AND LF)	hell
Onichocryptosissubungual hematoma Others	
	toes instep
EXTRA DETAILS	
EXTRAGETMENT	

 $\label{thm:continuous} \textbf{Table A.} \ \textbf{Foot temperature by sock type (technical/non-technical)}.$

Distance	Socks		P-value socks	P-value distance	e
(km)	T	NT	T-NT	Т	NT
			Dorsal temp (°C) R	F	
0	35.0	20.7	0.000*	(1)=0.000*	(1)=0.000*
14.5	36.2	32.3	0.000*	(2)=0.000*	(2)=0.000*
29.6	36.3	30.4	0.000*	(3)=0.101	(3)=0.413
			Dorsal temp (°C) L	F	
0	35.2	20.6	0.000*	(1)=0.000*	(1)=0.000*
14.5	36.2	32.4	0.000*	(2)=0.000*	(2)=0.000*
29.6	36.4	30.8	0.000*	(3)=0.101	(3)=0.053
			Plantar temp (°C)	RF	
0	34.9	21.2	0.000*	(1)=0.000*	(1)=0.000*
14.5	36.0	30.0	0.000*	(2)=0.000*	(2)=0.000*
29.6	36.2	29.8	0.000*	(3)=0.091	(3)=0.847
			Plantar temp (ºC) I	F	
0	34.9	21.3	0.000*	(1)=0.000*	(1)=0.000*
14.5	36.0	30.6	0.000*	(2)=0.000*	(2)=0.000*
29.6	36.2	29.8	0.000*	(3)=0.340	(3)=0.736

T=Technical, NT=Non-Technical, Km=Kilometres, Temp=Temperature, (°C)=Degrees centigrade (*)=Significant difference, RF=Right foot, LF=Left foot, (1)= Distance between 0-14.5 Km, (2)=Distance between 0-29.6 Km, (3)= between 14.5-29.6 Km.

Table B. Foot temperature by sock composition.

Distance (km)	Sock			P-value		P-value distance			
	T	S	С	T-S	T-C	S-C	T	S	С
				Dor	sal temp (°C) RF			
0	34.9	35.1	21.2	1.000	0.000*	0.000*	(1)=0.000*	(1)=0.000*	(1)=0.000*
14.5	36.1	36.2	32.3	1.000	0.000*	0.000*	(2)=0.000*	(2)=0.000*	(2)=0.000*
29.6	36.3	36.4	30.4	1.000	0.000*	0.000*	(3)=0.526	(3)=0.305	(3)=0.413
				Doi	rsal temp (°C) LF			
0	35.1	35.2	20.6	1.000	0.000*	0.000*	(1)=0.000*	(1)=0.002*	(1)=0.000*
14.5	36.3	36.1	32.4	0.417	0.000*	0.001*	(2)=0.000*	(2)=0.00*	(2)=0.000*
29.6	36.4	36.4	30.8	1.000	0.000*	0.000*	(3)=0.341	(3)=0.467	(3)=0.158
				Plar	ntar temp (°C) RF			
0	34.9	35.0	21.2	1.000	0.000*	0.000*	(1)=0.000*	(1)=0.000*	(1)=0.000*
14.5	35.7	36.1	30.0	0.228	0.000*	0.000*	(2)=0.000*	(2)=0.000*	(2)=0.000*
29.6	36.2	36.3	29.9	1.000	0.000*	0.000*	(3)=0.826	(3)=0.826	(3)=1.000
				Plar	ntar temp (°C) LF			
0	34.9	34.9	21.3	1.000	0.000*	0.000*	(1)=0.000*	(1)=0.000*	(1)=0.000*
14.5	36.2	35.8	30.6	0.105	0.000*	0.000*	(2)=0.000*	(2)=0.000*	(2)=0.000*
29.6	36.2	36.1	29.8	1.000	0.000*	0.000*	(3)=1.000	(3)=0.184	(3)=0.736

Km=Kilometres, T=Tierra, S=Set, C=Cotton, temp=Temperature, (°C)=Degrees centigrade, RF=Right foot, LF=Left foot, (*)=Significant difference, (1)= Distance between 0-14.5 Km, (2)= Distance between 0-29.6 Km, (3)= Distance between 14.5-29.6 Km.

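### No primary lesion class or half of the hike is designated and every lesion test runs at an uncorrected 0.05; of the 11 quoted lesion p-values, only the four technical-vs-cotton dermal results survive Holm

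*Combined protocol and SAP*

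**What the plan says.** The objective in section 3 is a trial "designed to analyze the influence of different types of socks (technical and non-technical) on the appearance of foot injuries". Section 4 lists skin, muscle and nail lesions as qualitative variables without ranking them, and gives sock type three levels: "Technical (Tierra) Technical (Set) Non-technical (Cotton". Its quantitative variables include "temperature of each foot measured in two aspects (plantar and dorsal), and perimeter of each foot, measured in four areas". Lesions are recorded separately for 0–14.5 km and 14.5–29.6 km.

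Section 6 treats the two kinds of variable differently. For Friedman and Kruskal-Wallis it says "both with Bonferroni correction for multiple testing was applied". For the qualitative variables, "chi-square or Fisher's exact test with a significance level of α = 0.05 was carried out", with no correction mentioned. It contains no primary outcome, hierarchy, exploratory label or sample-size basis.

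The Results then report, for the second half, "Differences were found between the percentage of dermal lesions among hikers wearing technical socks (21.1%) or non-technical socks (54.8%) (p-value=0.001"), and a similar first-half difference. For muscle lesions in the first half, "No difference between any of muscle lesions analyzed and technical and non-technical socks were found"; the second-half muscle and nail results are also null. Foot perimeter "did not reveal significant results (data not shown"). Alongside these stand several results for one sex, one foot and one lesion type, also reported as differences.

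**The concern.** With no lesion class or half designated, any lesion test below 0.05 can be read as the trial's answer, and the choice can be made after the results are seen. The pooled dermal result has the same standing as a left-foot blister result in men that goes against a technical sock (Set, p=0.021).

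The effect is visible in the Results. The text finds no muscle difference between technical and non-technical socks, yet the logistic-regression paragraph around Table 7 says non-technical socks carry the highest probability of both dermal and muscle lesions. The same paragraph says men are more likely than women to have skin lesions in the second half, although the second-half percentages are higher in women in both sock groups (68.8% vs 40%, and 26.3% vs 15.8%). Nothing in section 6 tells the reader which statement takes precedence.

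At stake is which of the reported differences the trial supports.

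**Working it through.** **1. Reproducing the printed p-values.** Counts are rebuilt from the printed percentages and tested with a two-sided Fisher exact test.

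| Skin lesion comparison | Counts | Recomputed | Printed |
|---|---|---|---|
| Technical vs cotton, 0–14.5 km | 5/76 vs 12/33 | 0.00023 | 0.000 |
| Technical vs cotton, 14.5–29.6 km | 16/76 vs 17/31 | 0.00107 | 0.001 |
| Same, women, 0–14.5 km | 4/38 vs 9/18 | 0.00211 | 0.002 |
| Same, women, 14.5–29.6 km | 10/38 vs 11/16 | 0.00568 | 0.006 |
| Women vs men, 0–14.5 km | 13/56 vs 4/53 | 0.0337 | 0.034 |

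The four second-half foot-specific values (0.018, 0.021, 0.023, 0.023) reproduce as uncorrected three-sock chi-square tests. The women's first-half blister values (0.050 right foot, 0.042 left foot) do not: from Table 3 the exact three-sock test gives 0.122 and 0.072, and chi-square gives 0.120 and 0.056. The printed values are used below, which favours the claims.

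**2. Family-wise error.** The Results quote 11 lesion p-values, five for the first half and six for the second. If independent, 1 − 0.95^11 = 0.431. With an assumed common correlation ρ, the rate is 1 − ∫φ(z)[Φ((c−√ρ z)/√(1−ρ)) − Φ((−c−√ρ z)/√(1−ρ))]^11 dz with c = 1.96. This gives 0.37 at ρ = 0.3, 0.30 at 0.5 and 0.22 at 0.7. Fisher's discreteness lowers the rate wherever that test is used.

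**3. Holm over the 11.** Sort the p-values, multiply by 11, 10, 9 and so on, and carry the running maximum forward.

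| Result | p | × | Adjusted |
|---|---|---|---|
| Skin, first half, all | 0.00023 | 11 | 0.0025 |
| Skin, second half, all | 0.00107 | 10 | 0.011 |
| Skin, first half, women | 0.00211 | 9 | 0.019 |
| Skin, second half, women | 0.00568 | 8 | 0.045 |
| Men, right-foot erosion | 0.018 | 7 | 0.126 |
| Men, left-foot blister | 0.021 | 6 | 0.126 |
| Women, reddened skin, each foot | 0.023, 0.023 | 5, 4 | 0.126 |
| Women vs men, first half | 0.034 | 3 | 0.126 |
| Women, left-foot blister | 0.042 | 2 | 0.126 |
| Women, right-foot blister | 0.050 | 1 | 0.126 |

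The printed 0.001, 0.002 and 0.006 give 0.010, 0.018 and 0.048 for rows two to four.

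**4. A smaller, hiker-level family.** Take technical vs cotton for skin and muscle in each half and nail in the second (no nail lesion occurred in the first): five tests. If independent at 0.05 each, 1 − 0.95^5 = 0.226. With attainable Fisher sizes of 0.042, 0.040, 0.035, 0.034 and 0.023 (assuming 28 and 15 hikers with muscle lesions and 3 with nail lesions) it is about 0.16. Holm gives first-half skin 0.000225 × 5 = 0.0011 and second-half skin 0.00107 × 4 = 0.0043, provided the muscle and nail p-values are larger, as the null reports suggest.

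**5. Second-half denominators.** 54.8% is 17/31, and the women's cotton columns in Table 4 are sixteenths, so the tables place both withdrawals among cotton wearers (33 − 2 = 31). Section 3 says both withdrew from technical socks, giving 74 and 33. Holding the event counts (an assumption), 16/74 vs 17/33 gives p = 0.0031 and 0.0031 × 4 = 0.012.

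**6. How firm the fourth survivor is.** Both withdrawals were women. With 36 and 18 women and the same events, 10/36 vs 11/18 gives p = 0.036, which no longer survives Holm over the 11. It also fails in a wider family: adding the four null results reported without p-values (men's skin in the second half, muscle in each half, nail in the second) makes 15 tests, and 0.00568 × 12 = 0.068. The two overall results and the women's first-half result survive both changes.

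**The case against.** The other side has real points, and most of them limit what can be claimed.

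A reader might infer that the trial also fails to name a contrast. It does name one: the objective sets technical against non-technical socks, and the pooled analyses use it. The three-sock tests are a breakdown.

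A reader might infer that every claim is made at full alpha. That holds for the lesion tests only. Bonferroni is stated for the temperature and perimeter tests, though its scope across endpoints is not given. Those variables are also not injuries, so they are weak candidates for the main outcome.

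A reader might see the null muscle and nail results as contradicting the dermal result. They are different outcomes, and the nail comparison has about three events. The one reversal, Set blisters on men's left feet, is a single cell of a sex-by-foot-by-lesion breakdown.

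A reader might take the five-test 22.6% as the error of the lesion analyses as reported. It describes a family constructed for this check, and is nearer 16% with Fisher's discreteness.

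Finally, the results are already known, so any family chosen now is post hoc and Holm cannot make it confirmatory. That stands, and the remedy has to say so. None of this supplies the missing designation or a correction for the lesion tests.

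**Conclusion.** The concern holds within limits. No primary lesion class or half is designated, and the lesion tests are uncorrected. The 11 quoted lesion tests carry a family-wise error of about 43% if independent, and about 22% to 37% at assumed correlations of 0.7 to 0.3. Seven of the 11 reported differences lose significance under Holm (adjusted 0.126). The four technical-vs-cotton dermal results keep it, at 0.0025 to 0.045.

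The stronger inference that the trial's main dermal finding is a multiplicity artefact is not supported: both overall results survive under every family and denominator tried. The women's second-half result is the fragile survivor. It depends on the tabulated denominators and on counting only tests with a printed p-value.

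These figures rest on counts rebuilt from percentages, on printed p-values for the foot-specific tests, and on reported null results that have no p-value. In particular, the muscle and nail nulls are reported by individual lesion, so the five-test family takes the any-lesion comparisons to be null too.

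**What to change.** In section 6:

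- State that no primary outcome or half of the hike was set in advance.
- Apply Holm at two-sided 0.05 to a named lesion family, for example technical vs cotton with one outcome per hiker, for skin, muscle and nail lesions by half. Report all adjusted p-values, including the muscle and nail ones that are not now printed, and acknowledge that the family was chosen after the results were known.
- Label the sex-, foot-, lesion-type-, three-sock and regression results exploratory, with no claim of significance.

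Before quoting an adjusted second-half p-value, reconcile section 3 with Table 4 and the 54.8% on which sock the two withdrawals wore. Over five tests the value is 0.0043 with 76 and 31 hikers, or about 0.012 with 74 and 33 if the event counts are unchanged. The overall dermal conclusion stands either way.

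The cost is a paragraph, a few re-run tests and relabelling; no new data are needed. The sex-, foot- and type-specific results lose their significance claims, including those in women that survive Holm over the 11, and the dermal p-values become slightly less favourable.
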